Novartis Research and Development

KJX839/Inclisiran

Clinical Trial Protocol MDCO-PCS-17-02 (CKJX839A12302) /
NCT03851705

A two-part (double-blind placebo-controlled/open-label) multicenter study to evaluate safety, tolerability, and efficacy of Inclisiran in subjects with homozygous familial hypercholesterolemia (HoFH)

ORION-5

Document type: Amended Protocol Version

EUDRACT number: 2018-000893-31

Version number: 01 (Clean)

Clinical Trial Phase: III

Release date: 08-Oct-2020 (content final)

Property of Novartis
Confidential

May not be used, divulged, published, or otherwise disclosed
without the consent of Novartis

Protocol Synopsis

Name of Sponsor/Company: Novartis
Name of Finished Product: Inclisiran for Injection (also referred to as KJX839)
Name of Active Ingredient: inclisiran sodium
Title of Study: A two-part (double-blind placebo-controlled/open-label) multicenter study to evaluate safety, tolerability, and efficacy of inclisiran in subjects with homozygous familial hypercholesterolemia (HoFH).
Phase of Development: III
Study Centers: Multicenter study
Central Facilities: This list is maintained by the Sponsor
Number of Subjects: At least 45 subjects; subjects randomized 2:1 to inclisiran: placebo.
Principal Investigator: Prof. [REDACTED] South Africa: [REDACTED]
Study Period: The estimated study period will be approximately 30 months from first subject enrolled in the study to last subject completed. This two-part study will include a 6-month double-blind placebo-controlled period to assess the safety, tolerability, and efficacy followed by an 18-month open-label single arm follow-up period.
Objectives:
Primary
The primary objective is to evaluate the effect of inclisiran treatment on:

Low-density lipoprotein cholesterol (LDL-C) levels at Day 150
Secondary
The secondary objectives are to evaluate the effect of inclisiran on:

LDL-C levels over timeProprotein convertase subtilisin/kexin type 9 (PCSK9) levels over timeOther lipids, lipoproteins, and apolipoproteinsIndividual responsiveness of subjects to inclisiran including proportion of subjects achieving prespecified global lipid guidelines for their indicationProportion of subjects with at least 30% LDL-C reduction from Day 1 over time
and to assess the

Safety and tolerability profile of inclisiran
[REDACTED]
Methodology:
Hypotheses: The primary hypothesis is that inclisiran, when used in combination with maximally tolerated statin therapy with or without ezetimibe, will be well-tolerated, will suppress PCSK9 synthesis assessed by the reduction in circulating PCSK9 >50% and will result in reduction of LDL-C, defined as mean percent change of >20% from Day 1 to Day 150 in subjects with HoFH.

Study Design: This study will be a Phase III, two-part (double-blind placebo-controlled/open-label) multicenter study to evaluate safety, tolerability, and efficacy in subjects with HoFH. This study has two sequential parts:

- Part 1: 6-month double-blind period in which subjects will be randomized to receive either inclisiran or placebo
- Part 2: 18-month open-label follow-up period; placebo-treated subjects from Part 1 will be transitioned to inclisiran and all subjects will participate in an open-label follow-up period of inclisiran only

Informed consent will be obtained from subjects before the initiation of any study-specific procedures.

Subjects who meet study inclusion/exclusion criteria will be instructed to continue to follow a National Cholesterol Education Program Adult Treatment Panel III (or comparable) diet and be required to maintain their current lipid lowering drug therapy for the duration of the study.

In this study, at least 45 subjects will be enrolled and randomized 2:1 to receive either inclisiran 300 mg SC or placebo on Day 1. Inclisiran and placebo will both be administered by a health care provider. Subjects will be observed in the clinic for at least 30 minutes post injection before being discharged. A second dose of inclisiran or placebo will be given at Day 90. After completion of Part 1, the inclisiran-treated subjects from Part 1 will receive a third dose of inclisiran administered on Day 270 and subsequent doses on Day 450 and Day 630. The placebo-treated subjects from Part 1 will be transitioned to inclisiran starting on Day 180 and the study will then transition to an open-label, single arm follow-up period of inclisiran only (Part 2). Placebo-treated subjects will receive their first dose of inclisiran on Day 180 and then subsequently receive a dose of inclisiran on Day 270, Day 450 and Day 630.

Subjects on a documented regimen of LDL or plasma apheresis will be allowed to continue their same regimen during the study using approximately the same frequency/timing as done at baseline. When apheresis is performed during a study visit (Dosing or Non-Dosing), blood samples for measurement of LDL-C, other lipids and laboratory assessments must be collected before the apheresis. When apheresis is performed during a Dosing Visit, dosing must occur just after completion of the apheresis. The next scheduled apheresis must not occur within 72 hours of injection of inclisiran. The subsequent study visit must occur at least 2 weeks after an apheresis was performed to ensure LDL-C levels measured during a study visit are not confounded by the apheresis (see [Figure 3-2](#) for details).

Safety results including adverse events (AEs), serious adverse events (SAEs), electrocardiograms (ECGs), concomitant medications, and clinical laboratory parameters will be assessed at specified visits through to the end of study (EOS) visit. All AEs must be reported. Adverse events or abnormal test findings will be followed until the event (or its sequelae) or the abnormal test finding resolves, stabilizes at a level acceptable to the Sponsor/Investigator and/or returns to baseline values. Other safety related information that should be reported as AEs include injection site reactions, neurological and psychiatric events, potential anaphylactic/hypersensitivity reactions, new onset of diabetes, and worsening of glycemic control.

Samples to detect formation of ADA (including binding and neutralizing antibodies) will be collected on Day 1 (prior to the injection) and at Day 90, Day 330, and Day 720.

The primary endpoint will be measured at Day 150 after which placebo-treated subjects will be transitioned to inclisiran on Day 180. All subjects will be enrolled in a long-term open-label follow-up period through Day 720 (EOS).

Efficacy (pharmacodynamic) assessments will include measurement of the effects of inclisiran on levels of LDL-C, other lipoproteins including total cholesterol (TC), triglycerides, high density lipoprotein cholesterol (HDL-C), non-HDL-C, very low density lipoprotein cholesterol (VLDL-C), apolipoprotein A1 (Apo-A1), apolipoprotein B (Apo-B), lipoprotein(a) [Lp(a)], and PCSK9. LDL-C is analyzed by beta-quantification (BQ) on Day 1, Day 150 and Day 720, and calculated using the Friedewald method on all visit days.

The safety and tolerability data from the double blind and open label part of the study will be reviewed by an Independent Data Monitoring Committee (IDMC) at pre-defined frequency. A recommendation will be made to continue, stop, or amend the study at any of these reviews.

Diagnosis and Main Criteria for Selection:

Subjects may be included if they meet all of the following inclusion criteria:

1. Males and females, ≥ 18 years of age with a diagnosis of HoFH by genetic confirmation or a clinical diagnosis based on a history of an untreated LDL-C concentration >500 mg/dL (13 mmol/L) together with either xanthoma before 10 years of age or evidence of heterozygous familial hypercholesterolemia in both parents (see [Appendix A](#))
2. Stable on a low-fat diet
3. Subjects on statins should be receiving a maximally tolerated dose. Maximum tolerated dose is defined as the maximum dose of statin that can be taken on a regular basis without intolerable adverse events. Intolerance to any dose of any statin must be documented as historical AEs attributed to the statin in question in the source documentation and on the Medical History page of the electronic case report form (eCRF) (see [Appendix B](#))
4. Subjects not receiving statins must have documented evidence of intolerance to at least two different statins (see [Appendix B](#))
5. Subjects on lipid-lowering therapies (such as statin and/or ezetimibe) should be on a stable dose for ≥ 30 days before screening with no planned medication or dose change during study participation
6. Fasting central laboratory LDL-C concentration ≥ 130 mg/dL (3.4 mmol/L)
7. Triglyceride concentration <400 mg/dL (4.5 mmol/L)
8. No current or planned renal dialysis or renal transplantation
9. Subjects on a documented regimen of LDL or plasma apheresis will be allowed to continue the apheresis during the study, if needed. The apheresis schedule should be maintained as deemed necessary and dosing should be scheduled to be done after apheresis. Administration of study drug should always occur at least 2 days following apheresis. Note: after implementation of protocol amendment 1, administration of study drug must either occur right after apheresis on the day of the study visit or at least 2 weeks following the last apheresis (see [Figure 3-2](#)).
10. Subjects must be willing and able to give written informed consent before initiation of any study-related procedures. The subject should be willing to comply with all required study procedures
11. Willing to follow all study procedures including adherence to dietary guidelines, study visits, fasting blood draws, and compliance with study treatment regimens

Subjects will be excluded from the study if any of the following exclusion criteria apply prior to randomization:

1. Use of Mipomersen or Lomitapide therapy within 5 months of screening
2. Treatment (within 90 days of screening) with monoclonal antibodies directed towards PCSK9
3. New York Heart Association (NYHA) class IV heart failure or last known left ventricular ejection fraction $<25\%$
4. Major adverse cardiovascular event within 3 months prior to randomization
5. Planned cardiac surgery or revascularization
6. Uncontrolled severe hypertension: systolic blood pressure >180 mmHg or diastolic blood pressure >110 mmHg prior to randomization despite anti-hypertensive therapy
7. Active liver disease defined as any known current infectious, neoplastic, or metabolic pathology of the liver or unexplained alanine aminotransferase (ALT), aspartate aminotransferase (AST), elevation $>3\times$ ULN, or total bilirubin $>2\times$ upper limit of normal (ULN) at screening confirmed by a repeat measurement at least 1 week apart
8. Severe concomitant noncardiovascular disease that carries the risk of reducing life expectancy to less than the duration of the trial
9. History of malignancy that required surgery (excluding local and wide-local excision), radiation therapy and/or commencement of systemic therapy as treatment during the 3 years prior to randomization
10. Females who are pregnant or nursing, or who are of childbearing potential and unwilling to use at least one acceptable effective method of contraception (eg, oral contraceptives, barrier methods, approved contraceptive implant, long-term injectable contraception, intrauterine device) for the entire duration of the study. Exemptions from this criterion:

- a. Women >2 years postmenopausal (defined as 1 year or longer since their last menstrual period) AND more than 55 years of age
- b. Postmenopausal women (as defined above) and less than 55 years of age with a negative pregnancy test within 24 hours of enrolment
- c. Women who are surgically sterilized at least 3 months prior to enrolment

11. Known history of alcohol and/or drug abuse within 5 years

12. Any condition that according to the investigator could interfere with the conduct of the study, such as but not limited to:

- a. Subjects who are unable to communicate or to cooperate with the investigator.
- b. Unable to understand the protocol requirements, instructions and study-related restrictions, the nature, scope, and possible consequences of the study (including subjects whose cooperation is doubtful due to drug abuse or alcohol dependency)
- c. Unlikely to comply with the protocol requirements, instructions, and study-related restrictions (eg, uncooperative attitude, inability to return for follow-up visits, and improbability of completing the study)
- d. Have any medical or surgical condition, which in the opinion of the investigator would put the subject at increased risk from participating in the study
- e. Persons directly involved in the conduct of the study

13. Any uncontrolled or serious disease, or any medical or surgical condition, that may either interfere with participation in the clinical study, and/or put the subject at significant risk (according to investigator's [or delegate] judgment) if he/she participates in the clinical study

14. Any underlying known disease, or surgical, physical, or medical condition that, in the opinion of the Investigator (or delegate), might interfere with the interpretation of clinical study results

15. Treatment with other investigational medicinal products or devices within 30 days or 5 half-lives of the screening visit, whichever is longer

16. Previous participation in the study

17. Hypersensitivity to any of the ingredients of inclisiran

Test Product, Dose and Mode of Administration: Inclisiran sodium 300 mg (equivalent to 284 mg inclisiran) will be administered as a single SC injection (1.5 mL) on Day 1, Day 90, and then every 180 days (Day 270, Day 450, and Day 630).

Duration of Treatment: The expected duration of the subjects' participation in the study will be approximately 734 days which includes screening, investigational product administration, and the EOS period to Day 720.

- Screening: Day -28 to -1
- Randomization, initiation of investigational product: Day 1
- Treatment Phase:
 - Dosing: Day 1 (inclisiran or placebo), Day 90 (inclisiran or placebo), Day 180 (placebo subjects switch to inclisiran), Day 270 (inclisiran), Day 450 (inclisiran), and Day 630 (inclisiran; final dose)
 - Additional clinic visits: Day 150, Day 180 (non-dosing visit for subjects randomized to the inclisiran arm), Day 330, Day 510, and Day 690
- EOS visit: Day 720 (90 days after final dose)

Reference Therapy, Dose, and Mode of Administration: Placebo will be administered as a single SC injection (1.5 mL) on Day 1 and Day 90. On Day 180, placebo-treated subjects will transition to receive inclisiran.

Criteria for Evaluation:

Efficacy:

The following endpoints will be examined:

Primary Endpoints:

Percent change in LDL-C from baseline to Day 150

Key Secondary Endpoint(s):

- Absolute change in LDL-C from baseline to Day 150
- Percentage change in Apo-B from baseline to Day 150.
- Percentage change in non-HDL-C from baseline to Day 150.
- Percentage change in total cholesterol from baseline to Day 150.
- Proportion of subjects in each group with $\geq 30\%$ LDL-C reduction from baseline at Day 150.

Other Secondary Endpoint(s):

- Percentage change and absolute change in LDL-C from baseline to each assessment time up to Day 720 (i.e., Days 90, 150, 180, 270, 330, 450, 510, 630, 690, and 720)
- Percentage change and absolute change from baseline to Days 90, 150, 180, 330, 510, 690, and 720 in PCSK9
- Percentage change and absolute change from baseline to Days 150, 180, 330, 510, 690, and 720 in total cholesterol, Apo-B, and non-HDL-C for subjects receiving inclisiran
- Individual responsiveness of subjects defined as the number of subjects reaching on treatment LDL-C levels of <25 mg/dL, <50 mg/dL, <70 mg/dL, and <100 mg/dL at Days 150, 180, 330, 510, 690, and 720 including proportion of subjects in each group who attain global lipid targets for their indication
- Proportion of subjects in each group with $\geq 20\%$ or $\geq 30\%$ LDL-C reduction from baseline at Days 150, 180, 330, 510, 690, and 720
- Absolute change and percentage change in other lipids, lipoproteins, apolipoproteins, and PCSK9 from baseline at each subsequent visit to Day 720

Safety: AEs, SAEs, ECGs, vital signs, clinical laboratory values (hematology, glycated hemoglobin A1C [HbA1C], coagulation testing, chemistry, high sensitivity C-reactive protein (hsCRP), and urinalysis), formation and subsequent characterization of anti-drug antibodies (ADA), and results of neurological examinations will be collected at specified visits through to the EOS visit. Collection of AEs/SAEs will occur throughout the study at each study visit and all AEs must be reported. Adverse events or abnormal test findings will be followed until the event (or its sequelae) or the abnormal test finding resolves, stabilizes at a level acceptable to the Sponsor/Investigator and/or returns to baseline values. Other safety related information that should be reported as AEs include injection site reactions, neurological and psychiatric events, potential anaphylactic/hypersensitivity reactions, new onset of diabetes, and worsening of glycemic control.

Samples to detect formation of ADA (including binding and neutralizing antibodies) will be collected on Day 1 (prior to the injection) and at Day 90, Day 330, and Day 720.

Statistical Methods:**Sample Size and Power:**

The sample size calculation was performed with the hypothesis that the difference of mean percent change from baseline to Day 150 between inclisiran and placebo will be >20% (20% standard deviation) in subjects with HoFH when treated with inclisiran. The sample size of at least 45 subjects (randomized 2:1 to inclisiran : placebo), with at least 30 subjects in the inclisiran arm, will provide >80% power to detect a 20% reduction of LDL-C levels from baseline in the inclisiran group compared to that in the placebo at one-sided significance level of 0.025 based on two-sample t-test.

Study Population:

Intent-to-Treat (ITT) population - All subjects randomized into the study will comprise the ITT population. Treatment classification will be based on the randomized treatment.

Safety Population – All subjects who received at least one dose of investigational product. Treatment classification will be based on the actual treatment received.

Modified Intent-to-Treat (mITT) Population – All randomized subjects who receive at least one dose of investigational product and have both the baseline and the 150 day follow-up LDL-C assessment will comprise the mITT population. Treatment classification will be based on the randomized treatment.

Unless specified otherwise, the ITT will be the primary analysis population for efficacy analysis and Safety population will be the primary population for safety analysis in this study. mITT population will be used to confirm the efficacy.

Statistical Analysis:

Statistical comparisons will only be performed for the Part 1 of the study. The statistical analysis for study Part 2 is descriptive.

Summary statistics for continuous variables will include the number of subjects, mean, median, standard deviation or standard error, minimum and maximum. For categorical variables, the frequency and percentage will be given.

The primary endpoint is the percent change from baseline in LDL-C following 150 days of treatment.

The primary analysis will be conducted using ANCOVA model based on the multiply imputed datasets (100 total) - Washout based approach. The ANCOVA model will include the fixed effect of treatment group (Inclisiran or placebo) and baseline LDL-C as a covariate. Treatment effects from these 100 ANCOVA analyses will then be combined using Rubin's method. The difference between treatment groups in mean change from baseline to Day 150 in LDL-C and corresponding two-sided 95% confidence interval will be provided. The p value for testing equal mean change from baseline to Day 150 in LDL-C will also be provided. For the key secondary endpoints, the efficacy analyses will be similar to the primary analysis of the primary efficacy endpoint, the ANCOVA model will be used on the multiply imputed datasets (100 total) - Washout based approach. Treatment effects from these 100 ANCOVA analyses will then be combined using Rubin's method.

Additionally sensitivity analysis including MMRM on imputed data using PMM and without imputation will be performed for both primary and key secondary endpoints except for the endpoint of $\geq 30\%$ LDL-C reduction from baseline to Day 150, which will be analyzed using the logistic regression model with treatment as the effect.

This study is sufficiently powered for the hypothesis testing in the primary and key secondary endpoints, all other endpoints are supportive hence no adjustment for multiplicity is planned.

Safety summaries will include the incidence of AEs, summaries of laboratory parameters, vital signs, and ECGs.

Table of contents

Protocol Synopsis	2
Table of contents.....	8
List of tables.....	12
List of figures.....	12
List of abbreviations	13
Amendment 1 (08-Oct-2020).....	16
1 Introduction.....	26

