HoFH	homozygous familial hypercholesterolemia
HR	heart rate
hsCRP	high sensitivity C-reactive protein
IB	Investigator's Brochure
ICH	International Conference on Harmonisation of Technical Requirements for Registration of Pharmaceuticals
IDMC	Independent Data Monitoring Committee
IFN- γ	interferon-gamma
IL6	interleukin 6
INR	International normalized ratio
IRB	Institutional Review Board
IRT	Interactive Response Technology
ITT	intent-to-treat
IV	Intravenous
L	Liter(s)
LDL	low density lipoprotein
LDL-C	low density lipoprotein cholesterol
LDLR	low density lipoprotein receptor
Lp(a)	lipoprotein(a)
<hr/>	
MCH	mean cell hemoglobin
MCHC	mean corpuscular hemoglobin concentration
MCV	mean corpuscular volume
MDCO	The Medicines Company
MedDRA	Medical Dictionary for Regulatory Activities
mg	Milligram
MI	myocardial infarction
MITT	Modified intent-to-treat
mL	milliliter(s)
mmHg	millimeters of mercury
mmol	Millimole
MMRM	mixed-effect models for repeated measures
mRNA	messenger ribonucleic acid
NYHA	New York Heart Association
PCS	potentially clinical significant
PCSK9	proprotein convertase subtilisin/kexin type 9
PD	pharmacodynamic
PEF	peak expiratory flow
PK	pharmacokinetic
PMM	Pattern-Mixture Model

PT	prothrombin time
RISC	RNA-induced silencing complex
RNA	ribonucleic acid
RNAi	ribonucleic acid interference
SAE	serious adverse event
SAP	Statistical Analysis Plan
SC	Subcutaneous
SD	standard deviation
siRNA	small interfering ribonucleic acid
SUSAR	suspected unexpected serious adverse reaction
$t_{1/2}$	terminal half-life
TBIL	total bilirubin
TC	total cholesterol
TEAE	treatment emergent adverse event
TNF- α	tumor necrosis factor-alpha
TTR	target transthyretin
ULN	upper limit of normal
US	United States
VLDL-C	very low density lipoprotein cholesterol
WHO	World Health Organization

Amendment 1 (08-Oct-2020)

Amendment rationale

The first subject for this trial was randomized in Feb 2019 and enrollment was completed in Sep 2019 (with 56 subjects enrolled). Part 1 (double-blind phase) of the trial was completed on 02-Mar-2020, when the last subject completed the Day 180 visit and treatment allocation was unblinded. At time of this amendment, 51 subjects are still on study treatment.

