1.2.2.2.3 Study ORION-2 (MDCO-PCS-16-02, CKJX839A12202)

ORION-2 (MDCO-PCS-16-02, CKJX839A12202; completed) was a Phase II, open label, single arm, multicenter pilot study in subjects with homozygous familial hypercholesterolemia. Four subjects were randomized and received open-label inclsiran sodium 300 mg SC on Day 1. The subsequent dosing interval was determined by PCSK9 level at Day 60 or 90 or rate of change of PCSK9 between Days 60 and 90. Three subjects received a second injection because mean serum PCSK9 levels were not suppressed by $> 70\%$ at Day 60 or 90, as compared to baseline.

Inclisiran treatment resulted in robust and durable reductions in PCSK9 levels in all four subjects treated at a dose of 300 mg SC. Three of the four subjects also had significantly reduced levels of LDL-C. One subject had a significant reduction in PCSK9 but not a concomitant reduction in LDL-C. The mean percentage LDL-C reduction from baseline was 12.3% and 21.0% at Day 90 and Day 180, respectively. The maximum reductions in LDL-C were at Day 120 for two subjects and at Day 150 for a third subject. Therefore, the second dose achieved a greater reduction in LDL-C than after the first dose.

The mean percentage PCSK9 reduction from baseline was 59.0% and 62.9% at Day 90 and Day 180, respectively. Decreases in other lipids, lipoproteins, and apolipoproteins were commensurate with the decreases in LDL-C.

No safety observations were noted and inclisiran was generally well tolerated. Three of the four subjects reported adverse events. There were no deaths and one SAE (unstable angina, which was not considered related to study drug). No subjects withdrew due to an adverse event and no adverse events at the injection site were reported.

A number of notable elevations chemistry parameters were observed. One subject with an elevated total bilirubin ($>1x$ ULN) at screening experienced a single elevation of total bilirubin $>2x$ ULN on Day 120. There were no ALT or AST elevations $>3 \times$ ULN or CK elevations $>5x$ ULN. None of the subjects developed anti-drug antibodies.

The results from this pilot study support the 300mg dose and dose regimen for the ongoing Phase III ORION-5 study in HoFH.

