3.4 Secondary Endpoints

[figure not shown]
The key secondary endpoints of this study are:

- Absolute change in LDL-C from baseline to Day 150
- Percentage change in Apo-B from baseline to Day 150.
- Percentage change in non-HDL-C from baseline to Day 150.
- Percentage change in total cholesterol from baseline to Day 150.
- Proportion of subjects in each group with $\geq 30\%$ LDL-C reduction from baseline at Day 150.

The other secondary endpoints of this study are:

- Percentage change and absolute change in LDL-C from baseline to each assessment time up to Day 720 (ie, Days 90, 150, 180, 270, 330, 450, 510, 630, 690, and 720)
- Percentage change and absolute change from baseline to Days 90, 150, 180, 330, 510, 690, and 720 in PCSK9
- Percentage change and absolute change from baseline to Days 150, 180, 330, 510, 690, and 720 in total cholesterol, Apo-B, and non-HDL-C for subjects receiving inclisiran
- Individual responsiveness of subjects defined as the number of subjects reaching on treatment LDL-C levels of <25 mg/dL, <50 mg/dL, <70 mg/dL, and <100 mg/dL at Days 150, 180, 330, 510, 690, and 720 including proportion of subjects in each group who attain global lipid targets for their indication
- Proportion of subjects in each group with greater or equal to 30% LDL-C reduction from baseline at Days 150, 180, 330, 510, 690, and 720

- Absolute change and percentage change in other lipids, lipoproteins, apolipoproteins, and PCSK9 from baseline at each subsequent visit to Day 720
- Safety and tolerability profile of inclisiran as measured by AEs, SAEs, vital signs, clinical laboratory values, ECG measurements and formation and subsequent characterization of anti-drug antibodies (ADA)

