10.1 Sample Size

The sample size calculation was performed with the hypothesis that the difference of mean percent change from baseline to Day 150 between inclisiran and placebo will be >20% (20% standard deviation) in subjects with HoFH when treated with inclisiran. The sample size of at least 45 subjects (randomized 2:1 to inclisiran : placebo), with at least 30 subjects in the inclisiran arm, will provide >80% power to detect a 20% reduction of LDL-C levels from baseline in the inclisiran group compared to that in the placebo at one-sided significance level of 0.025 based on two-sample t-test.

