10.4.3.1 Primary Efficacy Endpoints

The primary efficacy endpoint is percent change from baseline to Day 150 in LDL-C.

The primary analysis will be conducted using ANCOVA model based on the multiply imputed datasets (100 total). The ANCOVA model will include the fixed effect of treatment group (Inclisiran or placebo) and baseline LDL-C as a covariate. Treatment effects from these 100 ANCOVA analyses will then be combined using Rubin's method. The difference between treatment groups in mean change from baseline to Day 150 in LDL-C and corresponding two-sided 95% confidence interval will be provided. The p-value for testing equal mean change from baseline to Day 150 in LDL-C will also be provided.

The missing data imputation for primary analysis will be the Washout-model-based approach. The washout model can be thought of as a modified control-based Pattern-Mixture Model (PMM) that

will be used to explore the possibility of data missing not at random (MNAR) for subjects who discontinued the study early.

Sensitivity analysis for the primary efficacy endpoint will use Wilcoxon rank-sum test, a nonparametric analysis method, as well as the two-sample t-test.

Also, we will perform sensitivity analyses to explore the dropout pattern and its possible impact on treatment comparisons in order to support the robustness of the conclusion drawn from the primary analysis using data up to Day 180. Pattern-Mixture Model (PMM) will be used to check the robustness when data missing not at random (MNAR) for subjects who discontinued study treatment. A control-based pattern-mixture model will be utilized. Multiple imputation will be used to account for uncertainty in the imputation process and results from a Mixed-effects Model for Repeated Measures (MMRM) on the imputed datasets will be combined using Rubin's method. Furthermore, a tipping point analysis will be performed to search for the tipping point that reverses the study conclusion. In addition, an analysis based on a Mixed-effects Model for Repeated Measures (MMRM) without multiple imputation will be performed.

The primary analysis and sensitivity analyses will be performed on both ITT and mITT populations. Details of the sensitivity analysis specified above will be in the SAP.

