10.4.3.2 Secondary Efficacy Endpoints

For the first four key secondary endpoints, the following efficacy analyses will be performed on the ITT and mITT populations:

- Similar to the primary analysis of the primary efficacy endpoint, the ANCOVA model will be used on the multiply imputed datasets (100 total) – Washout based approach. Treatment effects from these 100 ANCOVA analyses will then be combined using Rubin's method.
- MMRM model will be used on the multiply imputed datasets (100 total) – PPM based imputation. Treatment effects from these 100 ANCOVA analyses will then be combined using Rubin's method
- Analysis based on a Mixed-effects Model for Repeated Measures (MMRM) without multiple imputation will be performed.

For the key secondary endpoint of $\geq 30\%$ LDL-C reduction from baseline to Day 150, a logistic regression model with treatment as the effect will be used, and the odds ratio and its 95% confidence interval will be provided. The multiply imputed datasets created from both the washout model and the control-based PMM will be utilized in this analysis.

For the other secondary endpoints specified in [Section 3.4](#), generally descriptive and graphical summaries by treatment group will be presented for the ITT population. The two-sided 95% confidence interval may be provided for continuous variables based on the MMRM model. Odds ratio and 95% confidence interval may be provided for binary variables. Nominal p-values may be provided when applicable. Details of the analyses for the secondary endpoints are specified in the SAP.

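### Does the synopsis's three-part primary hypothesis, with its 20% and 50% thresholds, undermine a primary analysis that only tests equal means?

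*Protocol*

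**What the plan says.** The Hypotheses paragraph of the synopsis joins three statements under the label of primary hypothesis: good tolerability, a PCSK9 reduction above 50%, and an LDL-C effect worded as "will result in reduction of LDL-C, defined as mean percent change of >20% from Day 1 to Day 150 in subjects with HoFH". It names no comparator.

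The rest of the protocol is narrower.

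- Section 2.1 (Primary Objective) concerns LDL-C at Day 150 only, and Section 3.3 makes percent change in LDL-C to Day 150 the primary endpoint.
- Section 10.4.3.1 specifies an ANCOVA with treatment and baseline LDL-C, a between-arm difference with a two-sided 95% confidence interval, and this test: "The p-value for testing equal mean change from baseline to Day 150 in LDL-C will also be provided". The synopsis says the same: "The p value for testing equal mean change from baseline to Day 150 in LDL-C will also be provided".
- Section 10.1 gives the 20% a comparator. It rests on the hypothesis that "the difference of mean percent change from baseline to Day 150 between inclisiran and placebo will be >20" percent, with an SD of 20%, and states more than 80% power from a two-sample t-test at one-sided 0.025.
- PCSK9 appears in Section 3.4 among the other secondary endpoints, as "Percentage change and absolute change from baseline to Days 90, 150, 180, 330, 510, 690, and 720 in PCSK9", with no 50% criterion. For that group, Section 10.4.3.2 says that "generally descriptive and graphical summaries by treatment group will be presented for the ITT population".
- Safety and tolerability are a secondary objective (Section 2.2) with no success criterion.

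**The concern.** A reader who takes the synopsis literally would expect the primary analysis to decide whether all three statements are true. It cannot. Rejecting equal means shows that the arms differ. It does not show an LDL-C effect above 20%, and it carries no information on PCSK9 or tolerability. The 20% also changes meaning: in the Hypotheses paragraph it is a change from Day 1, and in Section 10.1 it is a difference from placebo. The two diverge whenever placebo LDL-C moves.

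The stake is over-claiming. A significant primary result could be reported as confirming the primary hypothesis when the effect is well short of 20 points. The protocol's own pilot in this disease (Section 1.2.2.2.3) makes a smaller effect seem possible: "The mean percentage LDL-C reduction from baseline was 12.3% and 21.0% at Day 90 and Day 180, respectively".

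**Working it through.** **Inputs.** From Section 10.1: 30 inclisiran and 15 placebo subjects (45 at 2:1), SD 20 points, assumed difference 20 points, one-sided alpha 0.025, two-sample t-test. The Amendment 1 rationale gives 56 enrolled; the protocol does not give the split, so 37 and 19 is assumed from the 2:1 ratio. The calculation ignores any gain from the baseline covariate and any loss from imputation, because the protocol gives no figure for either.

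**Step 1: reproduce the stated power.**

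- SE = 20 × √(1/30 + 1/15) = 20 × √0.1 = 6.325
- Noncentrality = 20 / 6.325 = 3.162; df = 30 + 15 − 2 = 43; critical t = 2.0167
- Power = 87.1% (noncentral t), or 88.5% by the normal approximation

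Both satisfy the stated figure of more than 80%. It reproduces as a test of zero difference with a true difference of 20 points.

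**Step 2: check that 20 points cannot be the null value.** If the trial had to show a between-arm difference above 20 points, the observed difference would have to exceed 20 + 2.0167 × 6.325 = 32.8 points. Power would be 2.5% at a true 20 points and would reach 80% only near 38.1. This contradicts the stated power, so Section 10.1 can only mean 20 points as the planning assumption.

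**Step 3: what a significant result implies.**

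| | 30 vs 15 | 37 vs 19 (assumed) |
|---|---|---|
| SE | 6.325 | 5.645 |
| df; critical t | 43; 2.0167 | 54; 2.0049 |
| Smallest significant difference | 12.75 | 11.32 |
| P(significant), true 12.3 points | 47.7% | 57.2% |
| P(significant), true 15 points | 64.0% | 74.2% |
| P(significant), true 20 points | 87.1% | 93.6% |

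At a true 15 points with 30 and 15 subjects, about 42% of trials would be significant with an estimate below 20.

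**Step 4: is this peculiar to the trial?** No. The ratio of the smallest significant difference to the planning effect is 2.0167 / 3.162 = 0.64. Any test of zero difference powered at about 87% becomes significant at roughly two thirds of its planning effect. The table describes superiority tests in general and reveals no error in this one.

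**Step 5: the pilot.** The 12.3% is a Day 90 value from four subjects without a control arm. The same section puts the largest reductions at Day 120 for two subjects and Day 150 for a third, and says the second dose lowered LDL-C further than the first. ORION-5 measures its endpoint at Day 150, after the Day 90 dose. The pilot's later value, 21.0% at Day 180, lies close to the planning figure. Neither value is a difference from placebo. The pilot is too small to exclude an effect below 20 points, but the 12.3% is a poor guide to the Day 150 effect.

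**The case for a change.** The strongest case for a change is that the sentence is more than background. It stands under Hypotheses, is called primary, and defines its LDL-C part by a number. No other statement in the protocol is called the primary hypothesis. Section 10.1 again speaks of a hypothesis of more than 20%. Amendment 1 revised the primary analysis model and the key secondary endpoints but left this sentence as it was, and aligning it would cost only a few words.

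Part of this stands. The synopsis does not match the objective, endpoint and analysis, and the sentence would be better split into a tested hypothesis and a set of expectations.

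The consequence does not stand. An analyst following Sections 2.1, 3.3 and 10.4.3.1 has one primary test to run, and the synopsis gives no instruction for another. The missing comparator is supplied in Section 10.1 and in the synopsis's own sample size text. The objection to Section 10.1 is one of style, because the sentence there goes on to the power to detect a 20% reduction with a named test and alpha. PCSK9 and tolerability already sit under the secondary objectives, and Section 10.4.3.2 already allows a 95% interval for continuous secondary endpoints. No section says that rejecting equal means would prove the 20% or 50% figures, so the feared over-claim is a possible misuse in reporting and is not something the plan prescribes.

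**Conclusion.** The concern identifies a real inconsistency of wording, and no change to the plan follows. The Hypotheses paragraph is best read as the scientific expectation behind the trial; the hypothesis tested is a zero difference between inclisiran and placebo in mean percent change in LDL-C at Day 150. That test is identifiable, its type I error is unaffected, and its power is stated correctly (87.1% against more than 80%, for 30 and 15 subjects with an SD of 20).

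A significant result can indeed arise from an observed difference of about 12.8 points, or about 11.3 at the assumed 37 and 19. The planned 95% confidence interval, with an expected half-width of about 12.8 points at the planned size, is what tells a reader how far the data support 20 points.

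Timing also limits any benefit. Part 1 ended on 02-Mar-2020, "when the last subject completed the Day 180 visit and treatment allocation was unblinded", and this protocol version is dated 08-Oct-2020. Rewriting the primary hypothesis at that stage would change no result and would itself need to be labelled as made after unblinding. Following the plan as written leads to the same sound analysis.
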